9.1.3 Medical History

Relevant medical history, including history of current disease, other pertinent chronic illness history, and information regarding underlying diseases will be recorded at Baseline.

9.1.4 Adverse Events

Information regarding occurrence of adverse events will be captured throughout the study. Duration (start and stop dates and times), severity/grade, outcome, treatment and relation to the intervention will be recorded.

10 EVALUATIONS BY VISIT

10.1 Visit/Assessment 1: Baseline Survey Assessment (Month 0)

1. Review the study with the participant (participant's legal representative) and obtain written informed consent and HIPAA authorization and assent, if appropriate.
2. Assign the participant a unique screening number.
3. Record demographic data.
4. Record household composition data (number of household members and children).
5. Administer and record current housing situation and history of homelessness instruments, adapted from the Family Options Study and the California Statewide Survey on Homelessness.
6. Administer and record income and employment survey, adapted from the California Statewide Survey on Homelessness.
7. Record concomitant interventions in terms of receipt of assistance from other housing, social, and economic assistance programs.
8. Administer and record monthly expenditure amounts and categories, adapted from the Survey of Income and Participation.
9. Administer and record Financial Well-Being Scale, adapted from the Consumer Financial Protection Bureau (financial well-being).
10. Administer and record Material Hardship Survey, adapted from the Urban Institute Well-Being and Basic Needs and the Survey of Income and Program Participation (material hardship)
11. Administer and record the USDA Brief Food Security Survey (food security)
12. Administer and record healthcare utilization survey, adapted from the California Statewide Survey on Homelessness
13. Administer and record health conditions and functional status survey, adapted from the California Statewide Survey on Homelessness
14. Administer and record Short-Form 12 v2 (physical health)
15. Administer and record Kessler 6 (psychological health)
16. Administer and record the Generalized Self-Efficacy Scale (self-efficacy)
17. Administer and record the Brief Resilience Scale (resilience)
18. Administer and record the Perceived Stress Scale (perceived stress)

19. Administer and record the Confusion, Hubbub and Order Scale (household chaos)
20. Administer and record the Future Scale (aka the Adult Hope Scale) (agency)
21. Schedule participant for Visit 2 in 180-240 days
22. Randomize participant to study group
23. Connect participant with community partner organization (Sacred Heart Community Service) for further social service assessment and assistance (both control and intervention groups) and orientation/navigation for initiation of guaranteed income payments (intervention group)

10.2 Visit/Assessment 2: 6-Month Survey Assessment (Month 6)

1. Record any Adverse Experiences
2. Concomitant interventions review
3. Record changes in household composition
4. Administer and record current housing situation and history of homelessness instruments, adapted from the Family Options Study and the California Statewide Survey on Homelessness.
5. Administer and record income and employment survey, adapted from the California Statewide Survey on Homelessness.
6. Record concomitant interventions in terms of receipt of assistance from other housing, social, and economic assistance programs.
7. Administer and record monthly expenditure amounts and categories, adapted from the Survey of Income and Participation.
8. Administer and record Financial Well-Being Scale, adapted from the Consumer Financial Protection Bureau (financial well-being).
9. Administer and record Material Hardship Survey, adapted from the Urban Institute Well-Being and Basic Needs and the Survey of Income and Program Participation (material hardship)
10. Administer and record the USDA Brief Food Security Survey (food security)
11. Administer and record healthcare utilization survey, adapted from the California Statewide Survey on Homelessness
12. Administer and record health conditions and functional status survey, adapted from the California Statewide Survey on Homelessness
13. Administer and record Short-Form 12 v2 (physical health)
14. Administer and record Kessler 6 (psychological health)
15. Administer and record the Generalized Self-Efficacy Scale (self-efficacy)
16. Administer and record the Brief Resilience Scale (resilience)
17. Administer and record the Perceived Stress Scale (perceived stress)
18. Administer and record the Confusion, Hubbub and Order Scale (household chaos)
19. Administer and record the Future Scale (aka the Adult Hope Scale) (agency)

10.3 Visit/Assessment 3: 12-Month Survey Assessment (Month 12)

1. Record any Adverse Experiences
2. Concomitant interventions review
3. Record household composition data (number of household members and children).
4. Administer and record current housing situation and history of homelessness instruments, adapted from the Family Options Study and the California Statewide Survey on Homelessness.
5. Administer and record income and employment survey, adapted from the California Statewide Survey on Homelessness.
6. Record concomitant interventions in terms of receipt of assistance from other housing, social, and economic assistance programs.
7. Administer and record monthly expenditure amounts and categories, adapted from the Survey of Income and Participation.
8. Administer and record Financial Well-Being Scale, adapted from the Consumer Financial Protection Bureau (financial well-being).
9. Administer and record Material Hardship Survey, adapted from the Urban Institute Well-Being and Basic Needs and the Survey of Income and Program Participation (material hardship)
10. Administer and record the USDA Brief Food Security Survey (food security)
11. Administer and record healthcare utilization survey, adapted from the California Statewide Survey on Homelessness
12. Administer and record health conditions and functional status survey, adapted from the California Statewide Survey on Homelessness
13. Administer and record Short-Form 12 v2 (physical health)
14. Administer and record Kessler 6 (psychological health)
15. Administer and record the Generalized Self-Efficacy Scale (self-efficacy)
16. Administer and record the Brief Resilience Scale (resilience)
17. Administer and record the Perceived Stress Scale (perceived stress)
18. Administer and record the Confusion, Hubbub and Order Scale (household chaos)
19. Administer and record the Future Scale (aka the Adult Hope Scale) (agency)

10.4 Visit/Assessment 4: 18-Month Survey Assessment (Month 18)

1. Record any Adverse Experiences
2. Concomitant interventions review
3. Record household composition data (number of household members and children).
4. Administer and record current housing situation and history of homelessness instruments, adapted from the Family Options Study and the California Statewide Survey on Homelessness.
5. Administer and record income and employment survey, adapted from the California Statewide Survey on Homelessness.

6. Record concomitant interventions in terms of receipt of assistance from other housing, social, and economic assistance programs.
7. Administer and record monthly expenditure amounts and categories, adapted from the Survey of Income and Participation.
8. Administer and record Financial Well-Being Scale, adapted from the Consumer Financial Protection Bureau (financial well-being).
9. Administer and record Material Hardship Survey, adapted from the Urban Institute Well-Being and Basic Needs and the Survey of Income and Program Participation (material hardship)
10. Administer and record the USDA Brief Food Security Survey (food security)
11. Administer and record healthcare utilization survey, adapted from the California Statewide Survey on Homelessness
12. Administer and record health conditions and functional status survey, adapted from the California Statewide Survey on Homelessness
13. Administer and record Short-Form 12 v2 (physical health)
14. Administer and record Kessler 6 (psychological health)
15. Administer and record the Generalized Self-Efficacy Scale (self-efficacy)
16. Administer and record the Brief Resilience Scale (resilience)
17. Administer and record the Perceived Stress Scale (perceived stress)
18. Administer and record the Confusion, Hubbub and Order Scale (household chaos)
19. Administer and record the Future Scale (aka the Adult Hope Scale) (agency)

10.5 Visit/Assessment 5: 24-Month Assessment (Month 24)

1. Record any Adverse Experiences
2. Concomitant interventions review
3. Record household composition data (number of household members and children).
4. Administer and record current housing situation and history of homelessness instruments, adapted from the Family Options Study and the California Statewide Survey on Homelessness.
5. Administer and record income and employment survey, adapted from the California Statewide Survey on Homelessness.
6. Record concomitant interventions in terms of receipt of assistance from other housing, social, and economic assistance programs.
7. Administer and record monthly expenditure amounts and categories, adapted from the Survey of Income and Participation.
8. Administer and record Financial Well-Being Scale, adapted from the Consumer Financial Protection Bureau (financial well-being).
9. Administer and record Material Hardship Survey, adapted from the Urban Institute Well-Being and Basic Needs and the Survey of Income and Program Participation (material hardship)

10. Administer and record the USDA Brief Food Security Survey (food security)
11. Administer and record healthcare utilization survey, adapted from the California Statewide Survey on Homelessness
12. Administer and record health conditions and functional status survey, adapted from the California Statewide Survey on Homelessness
13. Administer and record Short-Form 12 v2 (physical health)
14. Administer and record Kessler 6 (psychological health)
15. Administer and record the Generalized Self-Efficacy Scale (self-efficacy)
16. Administer and record the Brief Resilience Scale (resilience)
17. Administer and record the Perceived Stress Scale (perceived stress)
18. Administer and record the Confusion, Hubbub and Order Scale (household chaos)
19. Administer and record the Future Scale (aka the Adult Hope Scale) (agency)

10.6 Visit/Assessment 6: 27-Month Assessment (Month 27)

1. Record any Adverse Experiences
2. Concomitant interventions review
3. Record household composition data (number of household members and children).
4. Administer and record current housing situation and history of homelessness instruments, adapted from the Family Options Study and the California Statewide Survey on Homelessness.
5. Administer and record income and employment survey, adapted from the California Statewide Survey on Homelessness.
6. Record concomitant interventions in terms of receipt of assistance from other housing, social, and economic assistance programs.
7. Administer and record monthly expenditure amounts and categories, adapted from the Survey of Income and Participation.
8. Administer and record Financial Well-Being Scale, adapted from the Consumer Financial Protection Bureau (financial well-being).
9. Administer and record Material Hardship Survey, adapted from the Urban Institute Well-Being and Basic Needs and the Survey of Income and Program Participation (material hardship)
10. Administer and record the USDA Brief Food Security Survey (food security)
11. Administer and record healthcare utilization survey, adapted from the California Statewide Survey on Homelessness
12. Administer and record health conditions and functional status survey, adapted from the California Statewide Survey on Homelessness
13. Administer and record Short-Form 12 v2 (physical health)
14. Administer and record Kessler 6 (psychological health)
15. Administer and record the Generalized Self-Efficacy Scale (self-efficacy)

16. Administer and record the Brief Resilience Scale (resilience)
17. Administer and record the Perceived Stress Scale (perceived stress)
18. Administer and record the Confusion, Hubbub and Order Scale (household chaos)
19. Administer and record the Future Scale (aka the Adult Hope Scale) (agency)

10.7 Visit/Assessment 7: 30-Month Assessment (Month 30)

1. Record any Adverse Experiences
2. Concomitant interventions review
3. Record household composition data (number of household members and children).
4. Administer and record current housing situation and history of homelessness instruments, adapted from the Family Options Study and the California Statewide Survey on Homelessness.
5. Administer and record income and employment survey, adapted from the California Statewide Survey on Homelessness.
6. Record concomitant interventions in terms of receipt of assistance from other housing, social, and economic assistance programs.
7. Administer and record monthly expenditure amounts and categories, adapted from the Survey of Income and Participation.
8. Administer and record Financial Well-Being Scale, adapted from the Consumer Financial Protection Bureau (financial well-being).
9. Administer and record Material Hardship Survey, adapted from the Urban Institute Well-Being and Basic Needs and the Survey of Income and Program Participation (material hardship)
10. Administer and record the USDA Brief Food Security Survey (food security)
11. Administer and record healthcare utilization survey, adapted from the California Statewide Survey on Homelessness
12. Administer and record health conditions and functional status survey, adapted from the California Statewide Survey on Homelessness
13. Administer and record Short-Form 12 v2 (physical health)
14. Administer and record Kessler 6 (psychological health)
15. Administer and record the Generalized Self-Efficacy Scale (self-efficacy)
16. Administer and record the Brief Resilience Scale (resilience)
17. Administer and record the Perceived Stress Scale (perceived stress)
18. Administer and record the Confusion, Hubbub and Order Scale (household chaos)
19. Administer and record the Future Scale (aka the Adult Hope Scale) (agency)

10.8 Visit/Assessment 8: 36-Month Assessment (Month 36)

1. Record any Adverse Experiences

2. Concomitant interventions review
3. Record household composition data (number of household members and children).
4. Administer and record current housing situation and history of homelessness instruments, adapted from the Family Options Study and the California Statewide Survey on Homelessness.
5. Administer and record income and employment survey, adapted from the California Statewide Survey on Homelessness.
6. Record concomitant interventions in terms of receipt of assistance from other housing, social, and economic assistance programs.
7. Administer and record monthly expenditure amounts and categories, adapted from the Survey of Income and Participation.
8. Administer and record Financial Well-Being Scale, adapted from the Consumer Financial Protection Bureau (financial well-being).
9. Administer and record Material Hardship Survey, adapted from the Urban Institute Well-Being and Basic Needs and the Survey of Income and Program Participation (material hardship)
10. Administer and record the USDA Brief Food Security Survey (food security)
11. Administer and record healthcare utilization survey, adapted from the California Statewide Survey on Homelessness
12. Administer and record health conditions and functional status survey, adapted from the California Statewide Survey on Homelessness
13. Administer and record Short-Form 12 v2 (physical health)
14. Administer and record Kessler 6 (psychological health)
15. Administer and record the Generalized Self-Efficacy Scale (self-efficacy)
16. Administer and record the Brief Resilience Scale (resilience)
17. Administer and record the Perceived Stress Scale (perceived stress)
18. Administer and record the Confusion, Hubbub and Order Scale (household chaos)
19. Administer and record the Future Scale (aka the Adult Hope Scale) (agency)

10.9 12-Month Qualitative Interview Assessment (between months 6-12, subset of 40 participants)

1. Record any Adverse Experiences
2. Conduct semi-structured interview on impact of homelessness and guaranteed income (if applicable) on household strain and well-being, decision-making, time scarcity and future planning

10.10 24-Month Qualitative Interview Assessment (between months 18-24, subset of 40 participants)

1. Record any Adverse Experiences

2. Conduct semi-structured interview on impact of homelessness and guaranteed income (if applicable) on household strain and well-being, decision-making, time scarcity and future planning

10.11 Early Withdrawal Visit/Assessment

1. Record any Adverse Experiences
2. Concomitant interventions review
3. Record household composition data (number of household members and children).
4. Administer and record current housing situation and history of homelessness instruments, adapted from the Family Options Study and the California Statewide Survey on Homelessness.
5. Administer and record income and employment survey, adapted from the California Statewide Survey on Homelessness.
6. Record concomitant interventions in terms of receipt of assistance from other housing, social, and economic assistance programs.
7. Administer and record monthly expenditure amounts and categories, adapted from the Survey of Income and Participation.
8. Administer and record Financial Well-Being Scale, adapted from the Consumer Financial Protection Bureau (financial well-being).
9. Administer and record Material Hardship Survey, adapted from the Urban Institute Well-Being and Basic Needs and the Survey of Income and Program Participation (material hardship)
10. Administer and record the USDA Brief Food Security Survey (food security)
11. Administer and record healthcare utilization survey, adapted from the California Statewide Survey on Homelessness
12. Administer and record health conditions and functional status survey, adapted from the California Statewide Survey on Homelessness
13. Administer and record Short-Form 12 v2 (physical health)
14. Administer and record Kessler 6 (psychological health)
15. Administer and record the Generalized Self-Efficacy Scale (self-efficacy)
16. Administer and record the Brief Resilience Scale (resilience)
17. Administer and record the Perceived Stress Scale (perceived stress)
18. Administer and record the Confusion, Hubbub and Order Scale (household chaos)
19. Administer and record the Future Scale (aka the Adult Hope Scale) (agency)

11 ADVERSE EXPERIENCE REPORTING AND DOCUMENTATION

11.1 Adverse Events

The study team will probe, via discussion with the participant, for the occurrence of adverse events (AEs) during each participant visit and record the information in the site's

source documents. Adverse events will be recorded in the patient CRF. Adverse events will be described by duration (start and stop dates and times), severity, outcome, treatment and relation to study intervention, or if unrelated, the cause. For this study, the primary potential adverse events of concern associated with the study intervention are potential loss of existing public benefits and assistance among participants, and increased income tax burden, similar to the risks that would be incurred by the general population in daily life who might experience a similar increase in overall household income.

12 DISCONTINUATION AND REPLACEMENT OF PARTICIPANTS

12.1 Early Discontinuation of Study Intervention

A participant may discontinue receipt of the study intervention (guaranteed income) and participation in the evaluation activities at any time if the participant, investigator, or sponsor feel that it is not in the participant's best interest to continue. The following is a list of possible reasons for study treatment discontinuation:

- Participant withdrawal of consent (or assent)
- Adverse event that in the opinion of the investigator would be in the best interest of the participant to discontinue study treatment
- Lost to follow-up
- Sponsor request for early termination of study

If a participant is withdrawn from treatment due to an adverse event, the participant will be followed and treated by the Investigator, study team, and community partners until the issue has resolved or stabilized (i.e., assistance applying for additional public benefits, assistance programs, and/or social services from local, county, state, and federal entities in case of the loss of benefits).

All participants who discontinue the study intervention will be encouraged to undergo an early discontinuation visit/assessment as soon as possible and then should be encouraged to complete all remaining scheduled assessments if possible.

All participants are free to withdraw from participation at any time, for any reason, specified or unspecified, and without prejudice.

Reasonable attempts will be made by the investigator to provide a reason for participant withdrawals. The reason for the participant's withdrawal from the study will be specified in the participant's source documents. Refer to Section 10 for early termination assessment procedures.

12.2 Withdrawal of Participants from the Study

A participant may withdraw from the study at any time if the participant, investigator or sponsor feel that it is not in the participant's best interest to continue. All participants are free to withdraw from participation at any time, for any reason, specified or unspecified, and without prejudice.

Reasonable attempts will be made by the investigator to provide a reason for participant withdrawals. The reason for the participant's withdrawal from the study will be specified

in the participant's source documents. As noted above, participants who discontinue study treatment early (i.e., they withdraw prior to the end of the 36-month study period) should have an early discontinuation assessment. Refer to Section 10 for early termination procedures assessment. Participants who withdraw after Visit/Assessment 4 but prior to Visit 5 should be encouraged to come in for a final visit (and the procedures to be followed would include those for their next scheduled visit).

12.3 Replacement of Participants

Participants who withdraw from the study intervention will not be replaced.

Participants who withdraw from the study will not be replaced.

12.4 Study Interruptions Due to Specific Circumstances

- a) If the participant is no longer able to act as a payee for guaranteed income due to incarceration, we will contact the designated secondary payee for recruitment, consent, and enrollment as a study participant so that they may continue survey and interview assessments on behalf of the household. Additionally, our community partners will transfer any remaining guaranteed income payments to the secondary payee so that households will continue to receive the income.
- b) In case of family separation, guaranteed income payments will continue to the adult who continues to reside with the children in the household.
- c) If families move out of Santa Clara County during the study period, they will be eligible to continue to participate in the study and will be eligible to continue to receive the guaranteed income periods for the duration of the study period as long as their contact information remains up to date. This is because moving from the area may be a positive outcome enabled by receipt of public assistance, benefits, and/or the guaranteed income that would be relevant to ascertain for the purpose of the study.
- d) If participants opt for early withdrawal from the study (i.e., participating in the surveys and interviews), they will still be eligible to receive guaranteed income payments as a form of economic assistance provided by the community partners. However, only participants who consent and enroll in the study will be eligible for initial randomization.

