4 STUDY DESIGN

4.1 Study Overview

This is a single-site, single-blinded randomized controlled trial. The community partner service organizations, Destination: Home SV and the ¡Sí Se Puede! Collective, have raised funds to provide unconditional cash assistance in the form of guaranteed income (GI) for a period of two years to 150 families with children experiencing homelessness in Santa Clara County and who are eligible for referral to rapid rehousing assistance programs (RRH). The partner service organizations are prioritizing assistance to those awaiting RRH referral given the current extended wait time for RRH services. Because there are far more families who are eligible for GI than there are available resources, 150 eligible families will be randomly selected to receive GI. From the pool of eligible families, we will also randomly select an additional 150 participants as matched controls for the purpose of evaluation.

Thus, we are planning for a total of 300 participants. Participants will be assigned to either the control (usual care) or intervention (guaranteed income) groups in random order. Evaluations will be taken at baseline and every 6 months monthly via in-person and/or telephone assessments.

Screening data will be reviewed to determine participant eligibility. Participants who meet all inclusion criteria and none of the exclusion criteria will be entered into the study.

The following treatment regimens will be used:

- Intervention – guaranteed income, consisting of a total of \$24,000 to be disbursed over 24 months. Participants may opt for either monthly (\$1,000/month) or hybrid (lump sum of \$6,500 the first month, then \$500/month x 11 months for a total of \$12,000 per

year) disbursement schedules, with the option to switch disbursement schedule after the first 12 months. Participants will also be invited to attend a Public Benefits Information Session to learn about public benefits and social assistance programs available to residents of Santa Clara County. Participation in this Benefits Information Session will be optional and not required for study participation.

- Control – usual care as per the partner service organizations. Participants will be invited to also attend a Public Benefits Information Session to learn about public benefits and social assistance programs available to residents of Santa Clara County. Participation in this Benefits Information Session will be optional and not required for study participation.

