8 STUDY INTERVENTIONS

8.1 Method of Assigning Participants to Treatment Groups

Up to 300 eligible participants will be randomly assigned to the guaranteed income group (intervention) or usual care (control group) using a computer-generated randomization scheme developed by the study team. Eligible participants will be referred by the community partners (DHSV and SSPC) to the study team for consent and enrollment into the study prior to randomization. Once participants are enrolled, they will undergo a baseline assessment before being randomly assigned to either the intervention or control group. Randomization will be stratified by referring community partner (DHSV vs SSPC). Group assignments will be known to our community partners at Sacred Heart Community Service, a neutral third community-based organization contracted by DHSV and SSPC to administer and provide support for the guaranteed income intervention; however, the core study team (investigators and core research staff at UCSF) will be blinded to group assignments.

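### Section 12.4(a) supplies a substitute survey respondent after incarceration only through the guaranteed-income payee role, so ascertainment of days homeless differs by arm in the affected households

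*Protocol*

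**What the plan says.** Protocol section 12.4(a) sets the trigger as "If the participant is no longer able to act as a payee for guaranteed income due to incarceration". The response is that "we will contact the designated secondary payee for recruitment, consent, and enrollment as a study participant", and the stated purpose is "so that they may continue survey and interview assessments on behalf of the household". A separate sentence covers the money: "our community partners will transfer any remaining guaranteed income payments to the secondary payee".

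The control arm is described in section 4.1 as "Control – usual care as per the partner service organizations". It includes no payments.

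Section 14.1 makes the study team's own surveys and structured interviews the primary dataset. Whoever answers the survey therefore supplies the data for days homeless, the primary endpoint in sections 5.1 and 14.6.

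On blinding, section 8.1 says "the core study team (investigators and core research staff at UCSF) will be blinded to group assignments". Section 8.2 exempts the biostatistician, a data liaison and a participant notification liaison, and keeps the blind until after database lock. Section 2.1 gives consent, surveys and interviews to trained research staff.

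**The concern.** Both the trigger and the substitute in 12.4(a) are defined by a role that only intervention households hold. When the enrolled adult of an intervention household is jailed, the household stays in follow-up through another adult. When the same happens in a control household, the trigger cannot apply, and no other section supplies a second respondent. This would remain so even if control families happened to name a second adult, because the event is worded as inability to receive payments.

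Two things are at stake. First, who reports the primary endpoint, and whether it is reported at all, depends on allocation after an event that is plausibly related to housing. Control data that were never collected cannot be recovered at the analysis stage. Second, the rule probably marks the affected households as intervention households to the staff who survey them.

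**Working it through.** **Text check: the same event in each arm**

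| Step | Intervention household | Control household |
|---|---|---|
| Enrolled adult is jailed | Trigger in 12.4(a) is met | Trigger cannot be met, as there is no payee |
| Substitute respondent | Secondary payee is enrolled | None named |
| Later surveys | Continue through the substitute | Not addressed |
| Visible to survey staff | Change of respondent to a payee | No equivalent change |

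In 12.4(a) *we* recruit, consent and enrol, while the community partners are named separately for moving the payments. *We* therefore reads most naturally as the study team. Set beside section 2.1 (research staff obtain consent and run surveys) and sections 8.1 and 8.2 (core staff blinded, three exempt roles), this makes disclosure of the arm in those households likely. It remains an inference from the text.

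**The plan's own figures**

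Inputs from section 14.6: SD 74.0, two-sided alpha 0.05, 150 per arm, or 110 per arm after 27% dropout. By the normal approximation, power = Φ(Δ / [SD × √(1/n₁ + 1/n₂)] − 1.96).

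- Δ = 24.0, n = 150 per arm: SE = 74 × √(2/150) = 8.54; 24.0/8.54 − 1.96 = 0.85; power 80.2%.
- Δ = 28.0, n = 110 per arm: SE = 74 × √(2/110) = 9.98; 28.0/9.98 − 1.96 = 0.85; power 80.1%.

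The stated 80% reproduces in both cases.

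**Size of the asymmetry (illustration)**

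The document gives no incarceration rate, so the following are assumptions:

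- A share q of each arm is affected.
- Intervention households are all retained, and the substitute reports accurately.
- Affected control households are all lost, on top of the 27% dropout.
- Other dropouts do not differ on average from those retained.
- Lost control households differ from retained ones by D days on average.

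The full control mean is then (retained mean) + q × D, while only the retained mean is observed. The arm difference shifts by q × D. The control number falls to 110 − 150q.

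| q | Control families lost (150q) | Control n | Power for 28.0 days | Shift, D = 37 (0.5 SD) | Shift, D = 74 (1 SD) | Shift, D = 148 (2 SD) |
|---|---|---|---|---|---|---|
| 1% | 1.5 | 108.5 | 79.9% | 0.37 | 0.74 | 1.48 |
| 2% | 3 | 107 | 79.6% | 0.74 | 1.48 | 2.96 |
| 5% | 7.5 | 102.5 | 78.7% | 1.85 | 3.70 | 7.40 |
| 10% | 15 | 95 | 77.1% | 3.70 | 7.40 | 14.80 |

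Example for q = 5%: SE = 74 × √(1/102.5 + 1/110) = 10.16; 28.0/10.16 − 1.96 = 0.80; power 78.7%.

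The sign of the shift follows the sign of D. If lost control families had more homeless days than retained ones, the control mean is understated and so is any benefit of the payments. If they had fewer, the reverse holds.

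**The case against.** The strongest reply is that this is a rare-event wording gap. Nothing in the protocol says that a jailed control participant is dropped. Incarceration is not withdrawal under sections 12.1 and 12.2, assessments may be done by telephone (4.1), administrative housing data are planned as a complement (14.1), and missing data are to be multiply imputed with a last-observation-carried-forward sensitivity analysis (14.3). All of this stands. Loss of affected control households is an assumption of the table above, and the protocol does not prescribe it. But none of these provisions gives control households the second respondent that intervention households receive, so the asymmetry remains.

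On blinding, an unblinded liaison could make the contact, and few households are involved. Allocation can also surface elsewhere: participants know their arm, income and assistance are asked about at every follow-up survey, adverse-event probing covers loss of benefits, and the qualitative interviews discuss the payments. So a reader should not conclude that the team learns the allocation of the trial as a whole. What stands is narrower. The text does not route this contact through a liaison, and with no equivalent in controls the change of respondent would itself be informative.

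Four stronger readings are tempting and are not supported:

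- *A shift as large as the detectable difference.* Multiplying 5% of households by 500 days gives 25 days, against the stated 24.0. But 500 days lies (500 − 52.3)/74.0 = 6.05 SD above the plan's own mean. The product also does not describe loss to follow-up, where only the difference between lost and retained households matters.
- *A contradiction with section 12.3.* That section says "Participants who withdraw from the study will not be replaced". It concerns withdrawal; 12.4(a) keeps the same household in follow-up after a different event.
- *A fault in 12.4(b).* It says "In case of family separation, guaranteed income payments will continue to the adult who continues to reside with the children in the household". This is a payment rule and enrols nobody. Whose housing is counted after separation can be settled in the statistical analysis plan.
- *A claim that multiple imputation must fail.* Section 14.3 states no missingness assumption, and the imputation model is ordinary content for the statistical analysis plan.

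**Conclusion.** The point holds. As written, 12.4(a) makes continued ascertainment of the primary endpoint after incarceration depend on an intervention-only role, and gives control households no matching route. It is a rule of trial conduct, so it has to be corrected in the protocol.

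The size is unknown and probably modest. With 1% to 10% of households affected and a 1 SD difference, the shift is about 0.7 to 7.4 days, before any imputation. It passes 7.4 days only where 10% of households are affected and the difference exceeds 1 SD, reaching 14.8 days at 2 SD. Power for 28.0 days stays between 77.1% and 79.9%, so the issue is bias in a subset and not loss of power. The rate, the size of the difference and the loss of control households are all assumptions. Disclosure of the arm is a close inference confined to the affected households.

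**What to change.** 1. At the baseline visit (section 10.1), before the randomization step, have every household in both arms name an alternate adult respondent. Household composition is already recorded at that visit.
2. Reword 12.4(a) so that incarceration of the enrolled adult, in either arm and regardless of payee status, leads to the same invitation: the alternate adult is asked to consent and complete the remaining assessments for the household. Keep the payment sentence separate and unchanged.
3. State that an unblinded liaison makes the first contact, and keep payee language out of anything that blinded survey staff see. Because the switch can then occur in both arms, a change of respondent no longer identifies the arm.

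The cost is one item on the baseline form, a short amendment, and a little extra consent work for a few control households. Other routes by which participants may disclose their arm remain.
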